14.4.1 Analysis of Primary Efficacy Endpoint

The primary endpoint is described in Section 9.1. The primary efficacy analysis is a random coefficient regression (random slopes and intercepts) model. Treatment and baseline FVC (mL) will be included as a covariate in the analysis model. Other covariates such as age, and gender will be included as covariates unless their inclusion violates model assumptions or impacts stability. Baseline FVC is defined as the FVC result recorded at Visit w0/baseline, unless missing in which case the latest FVC before randomization in the subject's chart result will be used.

The decrease in FVC is assumed to be linear within each subject over 52 weeks. The intercepts and slopes will be assumed to be normally distributed with arbitrary covariance matrix. The within-subject error will be assumed to be independent and normally distributed with mean zero and a common variance. The Kenward-Roger approximation will be used to estimate denominators degrees of freedom.

Section 14.8 details of the approaches to handling of missing data are given.

Significance tests will be based on least-squares means; p-values and two-sided 90% confidence intervals for the difference between the treatment groups will be presented. An intent-to-treat principle will be used. Analyses will be implemented using SAS® Version 9.4 or higher. The assumptions for the primary analysis of decline in FVC will be tested; details will be provided in the SAP. The primary analysis will be based on observed data (but including retrieved drop out

measurements) and will assume remaining missing data are missing at random. The effect of missing data will be investigated using multiple imputation methods which assume that subjects who discontinue treatment will no longer benefit from it in the future. See Section 14.8 for further details of these sensitivity analyses.

Subgroup analyses will be fully specified in the SAP and will include:

- Age
- Gender
- Race
- Ethnicity
- Previous treatment with pirfenidone and/or nintedanib
- Recruitment cohort (e.g., pre- or post- DSMB cutoff, and pre- or post-Protocol version 6.1_UK)

A cumulative distribution plot will be provided, showing the percentage of subjects by change from baseline in FVC in mL at week 52.

Data will be summarized graphically and using summary statistics.

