14.7 Randomization

Following the Protocol version 6.1_UK participants will be randomised in blocks to double-blind treatment in a 1:2 ratio (Placebo : GB0139 3 mg). The unbalanced randomisation is to maintain the same probability of allocation to placebo post-Protocol version 6.1_UK since this may impact participant enrolment. Note that prior to Protocol version 6.1_UK participants were randomized in blocks to double-blind treatment in a 1:1:1 ratio (GB0139 3 mg : GB0139 10 mg : Placebo) stratified by SoC.

The Sponsor will arrange for the randomization and the packaging and labelling of trial medication. The randomization list will be generated using a validated system, which involves a pseudo-random number generator so that the resulting treatment will be both reproducible and non-predictable. The block size will be documented in the CTR. Access to the codes will be controlled and documented.

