## 1.3 Study Populations

There are 3 populations of interest. These are as follows:

[figure not shown]
- **Primary Population** : Subjects recruited under the new design, plus those from the original design recruited to SoC2 (not being treated with nintedanib or pirfenidone prior to screening) and randomized to either placebo or 3mg GB0139.
- **SoC1 Population/Combination**: Subjects recruited under the original design to SoC1 (current treatment at baseline with nintedanib or pirfenidone).
- **SoC2 Population/Monotherapy**: Those subjects from the original design in the SoC2 stratum (not receiving nintedanib or pirfenidone at baseline), plus all subjects from

	Plus-Project Statistical Analysis Plan	
	Protocol Number: GALACTIC-1	Version: 1

the new design. SOC2/Monotherapy Population is the Primary Population plus SoC2 10 mg.

These populations are described visually in Figure 2 below.

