### 3.2 Randomization and Blinding

In the original design, within each SoC subpopulation (SoC1: subjects on nintedanib/pirfenidone at baseline, SoC2: subjects not treated with nintedanib/pirfenidone), subjects were randomized in blocks to double-blind treatment in a 1:1:1 ratio (GB0139 3 mg: GB0139 10 mg: Placebo).

For the updated design, there is no stratification and subjects are randomized in a 2:1 ratio GB0139 3mg: Placebo. The unbalanced randomization is to maintain the same probability of allocation to placebo post design change, since it is considered that this may facilitate participant enrollment.

The Sponsor arranged for the randomization and the packaging and labelling of trial medication. The randomization list will be generated using a validated system, which involves a pseudo-random number generator so that the resulting treatment will be both

	Plus-Project Statistical Analysis Plan	
	Protocol Number: GALACTIC-1	Version: 1

reproducible and non-predictable. The block size will be documented in the Clinical Study Report (CSR). Access to the codes will be controlled and documented.

This study is a double-blind study which will be maintained throughout the study, including the follow up period. The only exception to this is at the point of the design change, when the 10mg group in the SoC2 stratum had to be unblinded in order to withdraw them from the study early. Study medication is identified by a medication code number. Packaging and labelling will be otherwise identical. An Integrated Web Response System (IWRS) will be used to assign subjects to treatment groups at study start. The randomization code will be kept undisclosed up to database lock.

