### 7.2.2 Main Estimand and Analysis

The primary analysis will test for superiority of GB0139 3mg compared to Placebo (Plc) for the annual rate of decline in FVC in mL over 52 weeks in subjects not receiving pirfenidone or nintedanib at baseline in the mITT Set. The main estimand for the primary efficacy endpoint is as follows:

- Population: Primary Population, mITT set.
- Variable of interest: Change from baseline in FVC in mL over 52 weeks
- Intercurrent events:
  - Death: FVC attributed the lowest value recorded in the trial when a patient dies

	Plus-Project Statistical Analysis Plan	
	Protocol Number: GALACTIC-1	Version: 1

- Treatment Discontinuation: Analysis will include any FVC measurements after randomised treatment discontinuation
- Initiation of additional IPF therapy (nintedanib or pirfenidone): Analysis will include any FVC measurements after initiation of additional IPF therapy
- Summary measure: Comparison of slopes assessed through the treatment by time interaction.

The null hypothesis is:

$H_0$ : There is no difference in the annual rate of decline in FVC in mL between GB0139 3mg and Plc

The alternative hypothesis is:

$H_a$  : There is a difference in the annual rate of decline in FVC in mL between GB0139 3mg and Plc

A restricted maximum likelihood (REML) approach will be used, with a random coefficient regression (random slopes and intercepts) model fitted to test the hypotheses. The decrease in FVC is assumed to be linear within each subject over 52 weeks [5].

Baseline FVC and time will be fitted as continuous covariates. The treatment group and the interaction term for time by treatment group will be added as fixed effects. Random subject intercept and time effects will be fitted and will be assumed to be normally distributed with arbitrary covariance matrix. The within-subject errors will be assumed to be independent and normally distributed with mean zero and a common variance. The Kenward-Roger approximation will be used to estimate denominators degrees of freedom.

The statistical model will be as follows:

$$Y_{itk} = (\alpha + a_i + \tau_k) + \beta_f FVCb_i + (\gamma + \beta_3 T_3 + g_i) t + \varepsilon_{it}$$

where:

$Y_{itk}$  is the change from baseline measured for ith patient at time t (actual time) in treatment group k

$t$  is the time since randomization in years

$T_3 = 1$  if the subject is in the GB0139 3mg group, otherwise  $T_3 = 0$

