#### 7.2.2.4 Primary Estimand Sensitivity Analysis

A Mixed Model with Repeated Measures (MMRM) will be fitted to the change from baseline in FVC across all visits with data imputed at Week 52 per the primary estimand (i.e. Week 52 will be attributed the lowest value recorded in the trial when a patient dies). Treatment, visit, baseline FVC, and treatment-by-visit interaction will be fitted as fixed effects. A restricted maximum likelihood (REML) approach will be used, and an unstructured covariance structure shared across treatment groups will be used to model the within-subject errors. If the model fails to converge, a heterogeneous Toeplitz structure (TYPE=TOEPH option in PROC MIXED rather than TYPE=UN) will be used. The Kenward-Roger's correction to degrees of freedom will be applied.

If there are concerns regarding the amount of missing data for the primary estimand, a sensitivity analysis to test the robustness of the MAR assumption used in the main estimand analysis will be performed to assess the results with missing Week 52 FVC data. A multiple imputation approach will be used. Full details of the methods to be followed are given in Section 11.4 and 11.5.

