## 9. CHANGES TO STATISTICAL ANALYSIS FROM PROTOCOL

The following clarifications have been made compared to the statistical analysis documented in the protocol at the time of writing (Version 7.0, 28 January 2022):

The protocol stated that two separate sensitivity analyses would be carried out for the primary estimand, and a tipping point analysis. The tipping point analysis described was looking for the tipping point between two sensitivity analyses, rather than relating to the primary analysis, and so was considered not to be informative and was removed. The second sensitivity analysis was also removed.

The protocol stated that for the endpoint of time to death, if fewer than 5% of subjects experienced the event during the study then only frequencies per treatment group would be displayed and no formal statistical analysis would be performed. The threshold for deaths has been removed and time to death will be analyzed regardless of the number of events.

In the logistic regression analyses the Wald test will be used rather than a likelihood ratio test.

The protocol defined a subgroup of subjects recruited prior to Protocol version 6.0 vs subjects recruited post v6.0, which is also removed.

[figure not shown]

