## 11.5 SAS Code

### 11.5.1 Primary analysis

```
ods output estimates=tests tests3=fixed;
proc mixed data=adef;
  where paramcd='FVC';
  class subjid trt01pn;
  model cfb = base areltn trt01pn trt01pn*areltn /ddfm=kr s residual outp=resplot;
  random intercept areltn / sub = subjid type = un;
  estimate 'Plc Slope' areltn 1 trt01pn*areltn 1 0/cl;
  estimate '3mg Slope' areltn 1 trt01pn*areltn 0 1/cl;
  estimate 'Slope 3mg v Plc' trt01pn*areltn 1 -1/cl;
run;
```

where

subjid = Subject ID

trt01pn = Randomized treatment group (1=Placebo, 2= GB0139 3mg)

base=Baseline FVC for the subject

areltn = Years since first dose

cfb = Change from baseline in FVC

<mean baseline FVC> = the mean of the variable base across all records in the dataset FVC relating to the population of interest (i.e. all records to be included in the model)

	Plus-Project Statistical Analysis Plan	
	Protocol Number: GALACTIC-1	Version: 1

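### The primary FVC model pools a 1:1 cohort with a 2:1 cohort and has no cohort-by-time term: a modest bias risk (at most 8.6 mL/yr for an assumed 50 mL/yr cohort gap) that is cheap to remove

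*SAP*

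**What the plan says.** - **Pooled population.** SAP 1.3 defines the Primary Population as "Subjects recruited under the new design, plus those from the original design recruited to SoC2" and randomised to placebo or 3 mg.
- **Two allocation ratios.** Protocol 14.7: "Note that prior to Protocol version 6.1_UK participants were randomized in blocks to double-blind treatment in a 1:1:1 ratio". With the 10 mg arm set aside, that is 1:1 for the two arms compared. SAP 3.2: "For the updated design, there is no stratification and subjects are randomized in a 2:1 ratio GB0139 3mg: Placebo".
- **Primary model.** SAP 7.2.2: "The treatment group and the interaction term for time by treatment group will be added as fixed effects". The SAP 7.2.2 equation contains baseline FVC, time, treatment and treatment-by-time, with random intercepts and slopes. The code in SAP 11.5.1 matches it: "model cfb = base areltn trt01pn trt01pn*areltn /ddfm=kr s residual outp=resplot". Neither has a cohort term.
- **FVC sensitivity model.** SAP 7.2.2.4, for the MMRM: "Treatment, visit, baseline FVC, and treatment-by-visit interaction will be fitted as fixed effects". Again there is no cohort term.
- **Cohort subgroup.** Protocol 14.4.1 lists "Recruitment cohort (e.g., pre- or post- DSMB cutoff, and pre- or post-Protocol version 6.1_UK" among the subgroups, and Protocol 14.5 repeats it. SAP 9 states: "The protocol defined a subgroup of subjects recruited prior to Protocol version 6.0 vs subjects recruited post v6.0, which is also removed". No reason is given.
- **What remains by design part.** SAP 1.3 promises a table of population composition by part and treatment group. SAP 7.2.5.2 summarises time to antifibrotic initiation in original-design SoC2 subjects. Both are descriptive.

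**The concern.** Randomisation protects the comparison within each scheme, not across a pool of two schemes with different ratios. Placebo is half of the first cohort and a third of the second, so updated-design subjects are over-represented on 3 mg. If the cohorts decline at different rates, part of that difference is read as treatment effect. If the updated cohort declines faster, 3 mg looks worse than it is and power falls; if more slowly, 3 mg looks better.

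The documents show one relevant difference in care. SAP 4.5 recognises that some original-design subjects started nintedanib or pirfenidone while on study drug, and SAP 1.1 says both are prohibited in the revised study. The primary estimand keeps FVC values after such initiation. A second difference is possible but not shown: Protocol 8.3.1 allows screening after a 7-day washout, and the original rule on prior use is not in the supplied documents.

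**Working it through.** **Inputs.** Two-sided alpha 10%, difference 100 mL and SD 240 mL (Protocol 14.6, SAP 3.1). About 320 randomised under the original design less approximately 200 discontinued (SAP 1.1) leaves about 120. This is a proxy for the 1:1 cohort, because SoC2 subjects who had already completed week 52 also belong to the Primary Population. The figure 141 is the overall total in Protocol 6.2 but the enrolment into the modified design in SAP 1.1. I therefore use two mixes: 120 + 21 and 120 + 141. The slope gaps of 10, 25 and 50 mL/yr are assumptions.

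**The plan's own figure.** With 47 placebo and 94 on 3 mg, SE = 240 × √(1/47 + 1/94) = 42.88. Power = Φ(100/42.88 − 1.645) = 75.4%, which reproduces the stated 75%.

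**Imbalance between arms.** Let x be the updated-cohort share of the pool. The 3 mg arm is (3 + x)/6 of the pool and placebo (3 − x)/6. The updated-cohort share is then 4x/(3 + x) on 3 mg and 2x/(3 − x) on placebo. The difference between these peaks at 0.1716, when x = 0.515.

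**Formulas.** Bias = gap × difference in share. Pooled SE = 240 × √(1/n₃ + 1/n_P). Type I error = P(|Z + bias/SE| > 1.645). Cohort-adjusted SE = 240/√(n_orig/4 + 2n_new/9).

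| | 120 + 21 | 120 + 141 |
|---|---|---|
| 3 mg : placebo | 74 : 67 | 154 : 107 |
| Updated share, 3 mg | 14/74 = 0.189 | 94/154 = 0.610 |
| Updated share, placebo | 7/67 = 0.104 | 47/107 = 0.439 |
| Difference | 0.0847 | 0.1711 |
| Pooled SE (mL/yr) | 40.47 | 30.21 |
| Bias at 10 / 25 / 50 mL/yr | 0.8 / 2.1 / 4.2 | 1.7 / 4.3 / 8.6 |
| Two-sided type I error | 10.01 / 10.05 / 10.2% | 10.05 / 10.3 / 11.4% |
| Tail favouring 3 mg (nominal 5%), updated cohort 50 mL/yr slower | 6.2% | 8.7% |
| Power at 100 mL, no gap | 79.6% | 95.2% |
| Power at 100 mL, updated cohort 50 mL/yr faster | 76.5% | 91.7% |
| Cohort-adjusted SE | 40.76 (+0.7%) | 30.65 (+1.5%) |
| Power after adjustment, no gap | 79.1% | 94.7% |

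**Other mixes.** With 150 + 141 the difference is 0.171 and type I error at 50 mL/yr is 11.5%. More lopsided mixes give less bias: with 10 + 131, a 10 mL/yr gap gives 0.5 mL/yr. Over all splits of a total of 141, the power cost of adjustment peaks at 1.04 points (68 + 73: 78.6% to 77.5%).

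**Which term removes the bias.** I took the expected estimates with visits at weeks 4 to 52, a gap of 100 mL/yr and the 120 + 141 mix, assuming slope SD 200–240, intercept SD 1–100 and residual SD 100–120. In the random-coefficient model the bias is 17.1 mL/yr with no cohort term, still 17.1 with a cohort main effect only, and 0 with cohort-by-time. In the MMRM at week 52 it is 17.1, then 14.4–15.5, then 0 with cohort-by-visit. A simulation of the SAP model with an assumed 20% dropout and a 50 mL/yr gap gave a bias of 4.6 (120 + 21) and 8.7 (120 + 141), Monte Carlo SE about 0.3, in line with the formula.

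**Could the blinded review settle it?** The SE of the pooled cohort gap is 240 × √(1/n_orig + 1/n_new) = 56.8 or 29.8 mL/yr, so its 90% half-width is 93 or 49 mL/yr. It would probably expose an extreme gap but cannot exclude the gaps considered here. It also absorbs one sixth (2/3 − 1/2) of any treatment effect.

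**The case against.** The strongest case is that the problem is small and its likely direction conservative. Protocol 4.1 says the approved drugs approximately halve FVC decline. If original-design subjects had more of them, the updated cohort declines faster and 3 mg looks worse. In the 120 + 141 mix with a 50 mL/yr gap in that direction, the false-superiority tail falls from 5% to 2.7%. By this mechanism a 50 mL/yr gap is also demanding: halving the assumed 200 mL placebo decline is worth about 100 mL/yr, so about half of original-cohort follow-up would have to be on these drugs and none of the updated cohort's. SAP 1.1 says subjects taking them were discontinued at the design change, and Protocol 8.3.1 and 10.5 let updated-design subjects take them after stopping study drug. All of this stands, and it limits the size.

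It is also fair that other analyses touch the issue. Supplementary Analysis 1 and the per-protocol repeat address antifibrotic initiation, the never-treated analysis addresses washout, and SAP 1.3 and 7.2.5.2 give cohort-related descriptions. The removed subgroup was exploratory, and SAP 9 discloses its removal. None of these outputs adjusts the primary test, however, and the never-treated analysis reuses the same model.

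If co-administration acts differently on 3 mg and on placebo, that is effect heterogeneity, which a common cohort-by-time term does not remove. That limits what the fix can do but is no reason to leave it out.

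**Conclusion.** The omission is certain; its consequence is modest and cannot be sized from the documents. Bias is gap × at most 0.172. Over assumed gaps of 10 to 50 mL/yr it is at most 1.7 to 8.6 mL/yr, that is, at most 8.6% of the 100 mL target and 0.28 SE in the larger of the two mixes. The results rest on SD 240 mL, on the proxy of 120, and on which meaning of 141 applies; the two statements of 141 should be reconciled.

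A reader might infer that the plan materially inflates the chance of a false positive for 3 mg. The documents do not support that: no gap is reported, the type I error change is small over this range, and the one documented difference in care points more towards lost power. Nor do they support saying that no cohort output survives, or that the power cost is always 0.5 point. What stands is a gap in robustness that is cheap to close. It is worth correcting and does not invalidate the design.

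**What to change.** Before unblinding:

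1. Define cohort by the randomisation scheme used (1:1:1 original or 2:1 updated). This is known without treatment codes.
2. In SAP 7.2.2 and 11.5.1, add `cohort` to the CLASS statement and `cohort` and `cohort*areltn` to the MODEL statement. Put matching `cohort*areltn` weights, summing to 1, in the two per-arm slope ESTIMATE statements; the slope-difference statement needs none. A cohort main effect alone does not remove the bias.
3. In SAP 7.2.2.4, add cohort and cohort-by-visit to the FVC MMRM.
4. Restore the protocol's cohort subgroup as a descriptive check. It does not correct the primary estimate.

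Cohort adjustment of the logistic and Cox models is optional and depends on event counts; its cost was not calculated.

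The cost is SAP wording and two terms in each of two models. Power falls by about 0.5 point in the mixes shown and by at most about 1 point for any split of a total of 141. It stays above 75% in every split tried, although the stated 75% refers to a 47:94 trial and is not a like-for-like comparison.

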#### 7.2.2.1 Primary Endpoint Supporting Analyses

Supporting analyses will be carried out in the SoC1 / Combination and SoC2 / Monotherapy Populations. The estimands for these analyses differ from the primary estimand of Section 7.2.1 only in the population and the variable of interest.

In all supporting analyses, the variable of interest, in addition to the change from baseline in FVC over 52 weeks, is the change from baseline in FVC in mL over 26 weeks. Any FVC values post Day 232 will be omitted from these analyses. The estimated rate of decline in FVC in mL will be produced based on 26 weeks of data. This analysis will also be repeated for the Primary Population.

Separate analyses will be performed for each of the SoC1/ Combination and SoC2 / Monotherapy Populations in the mITT Set.

	Plus-Project Statistical Analysis Plan	
	Protocol Number: GALACTIC-1	Version: 1

All statistical analyses and graphical summaries will be as described in Section 7.2.1.

### 7.2.2.2 Subgroup Analysis

The primary analysis detailed in Section 7.2.1 will also be repeated by subgroup (separately for each subgroup factor of interest) for the Primary Population (52 week and 26 week endpoint) and the SoC1 / Combination Population (52 week and 26 week endpoint) in the mITT Set. The time by treatment group interaction will be replaced with a time by treatment group by subgroup interaction and fixed effect for the subgroup factor will also be added. The effect on slope between treatments will be assessed within each level of the subgroup.

### 7.2.2.3 Supplementary Analysis

Supplementary analyses of the primary efficacy endpoint in the Primary Population will be performed as follows:

Supplementary Analysis	Analysis Set	Handling of intercurrent events		
		Death	Treatment discontinuation	Initiation of additional IPF therapy
1	mITT Set, Primary Population	FVC attributed lowest value recorded in the trial when a patient dies	Analysis will exclude all available FVC measurements after randomized treatment discontinuation	Analysis will exclude all available FVC measurements after initiation of additional IPF therapy
2	mITT Set, Primary Population	FVC attributed 0 when a patient dies	Analysis will include all available FVC measurements after randomized treatment discontinuation	Analysis will include all available FVC measurements after initiation of additional IPF therapy

	Plus-Project Statistical Analysis Plan	
	Protocol Number: GALACTIC-1	Version: 1

#### 7.2.2.4 Primary Estimand Sensitivity Analysis

A Mixed Model with Repeated Measures (MMRM) will be fitted to the change from baseline in FVC across all visits with data imputed at Week 52 per the primary estimand (i.e. Week 52 will be attributed the lowest value recorded in the trial when a patient dies). Treatment, visit, baseline FVC, and treatment-by-visit interaction will be fitted as fixed effects. A restricted maximum likelihood (REML) approach will be used, and an unstructured covariance structure shared across treatment groups will be used to model the within-subject errors. If the model fails to converge, a heterogeneous Toeplitz structure (TYPE=TOEPH option in PROC MIXED rather than TYPE=UN) will be used. The Kenward-Roger's correction to degrees of freedom will be applied.

If there are concerns regarding the amount of missing data for the primary estimand, a sensitivity analysis to test the robustness of the MAR assumption used in the main estimand analysis will be performed to assess the results with missing Week 52 FVC data. A multiple imputation approach will be used. Full details of the methods to be followed are given in Section 11.4 and 11.5.

